## **AIMS AND OBJECTIVES**

The study was designed as a prospective randomized case control study involving patients who were subjected to laparoscopic cholecystectomy in Unit I in the Department of Surgery, Jawaharlal Nehru Medical College, Aligarh Muslim University, Aligarh. The duration of study was 36 months.

The primary objective of this study was to study and assess the effect and impact of using the local anesthetic ropivacaine, over controls, on the intensity of post-operative pain in patients undergoing laparoscopic cholecystectomy; and to compare and assess the optimal site i.e. intraincisional v/s intraperitoneal of using local anesthetic (ropivacaine) for better post-laparoscopic cholecystectomy pain relief.

The secondary objectives of this study included

1. To identify the component of pain that is dominant after laparoscopic cholecystectomy.
2. To strive for making laparoscopic cholecystectomy a truly day case procedure in the public setup of developing countries like ours using this cheap drug i.e. ropivacaine.
3. To appreciate any emerging new trends in the epidemiology of cholelithiasis in North India.

## **MATERIALS AND METHODS**

The study was designed as a prospective randomized case control study involving patients who were subjected to LC in a single unit by a single surgeon in the Department of Surgery of a tertiary teaching government institute over a period of 36 months. Ethical approval was provided by the Ethical Committee of the University and was conducted in accordance with guidelines of 'Good Clinical Practice' and the 'Declaration of Helsinki'. Written informed consent was taken from all patients. The drug used for the study was 'Ropivacaine 0.2%' (Injection Ropin 0.2 %, Neon Laboratories Ltd., Mumbai, India) which is dispensed as a 20 ml ampoule. Ropivacaine is a United States-Food and Drug Administration (US-FDA) approved drug [FDA Application No. – (NDA) 020533] approved on 24/09/1996 [14] and has increasingly been used for infiltration anesthesia.

### **Inclusion Criteria**

All patients in the age group of 15-80 years conferring to Grade I or II of American Society of Anesthesiologists (ASA) physical status classification system, undergoing elective LC for symptomatic cholelithiasis by a single surgeon, were included in this study.

### **Exclusion Criteria**

Patients with known allergic reactions to LAs; cases that were converted to open cholecystectomy, as well as patients with major intra-operative complications; patients suffering from acute cholecystitis, empyema or malignancy of gall bladder, having history of chronic pain or those taking frequent analgesics or opioids preoperatively; patients with peptic ulceration, bleeding disorders, impaired renal and/or hepatic function, and sensitivity to NSAIDs or opioids. patients in whom gall bladder (GB) stones are found incidentally on ultrasonography (USG) (asymptomatic cholelithiasis); patients suffering from severe chronic

medical diseases and morbid obesity and patients unable to comprehend instructions or having communication problems were excluded from the study.

### **Study Design and Study Groups**

It was a prospective randomized case control triple blind study in which neither the patient nor the investigator i.e. myself, nor the operating surgeon knew whether the drug would be used or not; and if the drug is going to be used, what would be its location. Patients were, thus, divided into 3 groups – Controls: those who did not receive any drug but received normal saline (NS) at both sites, that is, intraperitoneally as well as intraincisionally; Intraperitoneal Ropivacaine group (IPR group): those who were given ropivacaine intraperitoneally and NS intraincisionally; and Intraincisional Ropivacaine group (IIR group): those who were given ropivacaine by infiltrating it locally at the skin incision site and given NS intraperitoneally.

### **Methodology**

During initial outpatient visits, the patients were fully assessed and a confirmed diagnosis was made on the basis of USG abdomen. In patients identified to having a recent episode of acute cholecystitis, an interval laparoscopic cholecystectomy after at least 6 weeks or later was done. Upon admission, patients were explained about the study and an informed consent was taken for participation in the study. Pain was assessed at 5 points of time in the post-operative period, that is, at 30 minutes (0.5 hour), 4 hour, 8 hour, 12 hour and 24 hour. Pain was assessed by both objective and subjective methods. The frequency of extra doses of analgesics (rescue analgesia) given over and above the standard analgesia was also noted. The different pain scales used were-

#### *A. Subjective Scales*

1. Visual Analog Scale (VAS) – A 10 cm line was used and patient was told to mark on it using a pen regarding the pain perceived by him/her.
2. 11 Point Numeric Rating Scale (NRS-11/NRS) – Patient was asked to assign a number to pain, what he/she think was appropriate to describe the pain.

**0-None; 1, 2, 3-Mild; 4, 5, 6-Moderate; 7, 8, 9, 10-Severe**

[figure not shown]
3. Visual Descriptor Scale (VDS) – A 7 point subjective scale in which patient was told to indicate it verbally about the perception of pain as experienced.

**No Pain / Slight Pain / Mild Pain / Moderate Pain / Severe Pain / Extreme Pain /  
The Most Intense Pain Imaginable**

कोई दर्द नहीं / बिल्कुल कम दर्द / कम दर्द / ठीक ठाक दर्द / तेज़ दर्द / बहुत तेज़ दर्द / असहनीय दर्द (in Hindi dialect)

#### *B. Objective Scales*

1. Faces Pain Scale – Revised (FPS-R) – This is an objective method of pain assessment in which facial expressions of the patient are assessed by the investigator, as depicted in the Figure 1 and scored accordingly.

2. Activity Tolerance Scale (ATS) – This is a combined objective and subjective method in which patient was asked subjectively for the below mentioned 5 grades of activity and the criterion told by patient was further objectively assessed by the investigator. By convention, this scale was not used to assess the patient at 30 minutes post-operative hour as all the patients remained in the recovery room at that time on the stretcher.

**No Pain / Can Be Ignored / Interferes With Task / Interferes With Concentration /  
Interferes With Basic Needs / Complete Bed Rest Required**

Patients were explained about the usage of the subjective pain scales and how to convey them to investigator. The objective pain scales were assessed by the investigator.

After routine standardized pre-operative evaluation, patients were shifted to operating room (OR) where they were made to choose from 3 pre-formed envelopes. These contained the information as to in what study group, the patients would belong to. The chosen envelope was then given to an independent OR attendant from a different OR, who then prepared one 20 ml and one 5 ml syringe. The 20 ml syringe either contained 20 ml of undiluted drug or 20 ml of NS depending upon the group. Similarly, the 5 ml syringe either contained 5 ml of undiluted drug or 5 ml of NS, again depending upon the group. Thus for control group, both syringes contained NS. For IPR group, 20 ml syringe contained the drug while 5 ml syringe contained NS. In IIR group, the 20 ml syringe contained NS while 5 ml syringe contained the drug. Thus all patients received intraperitoneal instillation as well as intraincisional infiltration at all points of time but nobody in the OR knew what is being given. Patient's name was written on the envelope and it was put in a locker. The envelopes were opened only after completion of study.

**Anesthetic Technique Protocol**

All patients received the same anesthetic technique. Anesthesia was induced with intravenous (IV) fentanyl  $1.5 \mu\text{g}/\text{kg}$ , propofol  $2 \text{ mg}/\text{kg}$ , and atracurium  $0.6 \text{ mg}/\text{kg}$ . Fentanyl was used for pain relief because it has a duration of analgesic action of 30 – 60 minutes [15] so it was not likely to affect the post-operative assessment of pain. After tracheal intubation, patient's lungs were mechanically ventilated and anesthesia was maintained with 60% nitrous oxide, oxygen, and one minimum alveolar concentration (MAC) isoflurane. A further bolus of fentanyl  $50 \mu\text{g}$  was given after 45 min of the initial dose or earlier if heart rate or BP increased by more than

20% of baseline value after incision. At the end of the surgery, residual neuromuscular blockade was antagonized with IV neostigmine 2.5 mg and glycopyrrolate 0.5 mg.

### **Operative Technique Protocol**

All the operations were performed by a single surgeon so the basic operative technique was similar in all the patients. A standard 4 port laparoscopic cholecystectomy (LC) was performed in all patients. A 10 mm horizontal skin incision was made at the superior aspect of the umbilicus and then deepened through the subcutaneous fat to the anterior rectus sheath. The infra-umbilical skin was pinched up with the left hand along with the underlying soft tissue (to avoid injury to viscera and bowel especially in case of any adhesions). A veress needle was inserted through the incision with the right hand, directed towards the midline. The veress needle was connected to the insufflator. Carbon dioxide (CO2) was insufflated into peritoneal cavity at the rate of 2 litres/min, upto a pressure of 10 mm of Hg. Veress needle was then removed. A 10 mm bladed trocar with sheath was placed at the umbilical port. The trocar was removed keeping the sheath in place. Insufflation of CO2 was initiated at the rate of 2 litres/min, upto a maximum pressure of 12-14 mm Hg. The gas flow rate was then kept at 6 litres/min during the procedure. The 10 mm epigastric port incision and the 5 mm right midclavicular and right anterior axillary incisions were given under vision.

At the end of procedure, intraperitoneal instillation was done using the irrigation apparatus under the right hemi-dome of diaphragm and in the GB fossa. The amount of intraperitoneal instillation was kept at 1ml/cm of length for uniformity of comparison at the 2 locations. Cassart et al., 1997 in their study calculated the total length of diaphragm ( $L_{di}$ ) at total lung capacity (TLC) to be  $44.1 \pm 1.6$  cm (right > left) and length of dome of diaphragm ( $L_{do}$ ) at TLC to be  $32.6 \pm 0.7$  (right > left) in control subjects. He also found out that  $L_{do}$  does not change in patients of COPD significantly; however  $L_{di}$  decreases significantly in patients suffering from

COPD. Taking a rough estimate of the length of dome of diaphragm at TLC, and since right hemi-dome is larger than the left, we took the length of right hemi-dome to be roughly 16 cm and thus used 16 ml intraperitoneal instillation along the right hemi dome. We also used 4 ml of solution in the GB fossa.

If a patient needed to be inserted a drain, a suction drain no. 12 was inserted through the lateral 5 mm port and it had to be blocked for half an hour to prevent the escape of solution into the drain. In such patients, thus, drain was opened only at the time when first observation was made. All of the skin incisions were closed with 3-0 non-absorbable monofilament nylon suture on cutting needle, followed by aseptic dressing. Intraincisional infiltration was done using the standardized amount i.e. 1ml/cm of length of incision. For this, length of the incision site was measured using a scale and the drug was infiltrated accordingly. Thus, if a port had to be increased to 12 mm for some reason, 1.2 ml of intraincisional infiltration was used. This ensured the uniformity of drug dosage used in the IPR and IIR groups. Duration of surgery was measured from the time of first incision to the final stitch taken at port sites.

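### The 1 ml/cm rule matches the nominal rate at the two sites, not the drug dosage: IPR patients receive 40 mg of ropivacaine and IIR patients about 6 mg (at most 10 mg)

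*Protocol*

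**What the plan says.** The Protocol's Materials and Methods section names the drug as ropivacaine 0.2%. The syringe description (Methodology, end of Objective Scales) says it was used undiluted. In the IPR group the drug is in the 20 ml syringe and saline in the 5 ml syringe; in the IIR group this is reversed.

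Operative Technique Protocol sets the volumes. For the peritoneum: "The amount of intraperitoneal instillation was kept at 1ml/cm of length for uniformity of comparison at the 2 locations". The volume under the diaphragm comes from an estimate: "we took the length of right hemi-dome to be roughly 16 cm and thus used 16 ml intraperitoneal instillation". A further volume is added without a length: "We also used 4 ml of solution in the GB fossa".

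For the ports: "Intraincisional infiltration was done using the standardized amount i.e. 1ml/cm of length of incision". Each incision was measured: "For this, length of the incision site was measured using a scale and the drug was infiltrated accordingly". A worked example follows: "Thus, if a port had to be increased to 12 mm for some reason, 1.2 ml of intraincisional infiltration was used". The section then draws the conclusion at issue: "This ensured the uniformity of drug dosage used in the IPR and IIR groups".

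**The concern.** The concluding sentence speaks of dosage in the two groups, and a reader would reasonably take it to mean that the groups received the same amount of drug. The volumes in the same section and in the syringe description show that they did not.

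This matters because Aims and Objectives makes the choice between the intraincisional and intraperitoneal sites part of the primary objective. IPR and IIR differ in total dose as well as in site, while the sentence tells the reader that dose is not a rival explanation. The effect depends on the result:

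- If IPR is better, the advantage may come from site, from dose, or from both.
- If the two are similar, the larger IPR dose may be hiding a site advantage for IIR.
- If IIR is better, a higher total dose cannot be the reason.

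The comparison of each active group with control is not affected, because controls receive saline at both sites under the same volume rules.

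**Working it through.** **Inputs**

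- Concentration: 0.2% (Materials and Methods), which is 2 mg/ml by the standard weight/volume conversion; undiluted (Methodology).
- Intraperitoneal volumes: 16 ml hemi-dome, 4 ml gall bladder fossa (Operative Technique Protocol).
- Incisions: umbilical 10 mm, epigastric 10 mm, midclavicular 5 mm, anterior axillary 5 mm (Operative Technique Protocol).
- Infiltration rate: 1 ml/cm (Operative Technique Protocol).
- Syringe limits: 20 ml and 5 ml (Methodology).

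**Reproducing the plan's own figure.** The intraperitoneal volume is 16 + 4 = 20 ml, which agrees with the 20 ml syringe.

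**Nominal rate.** 1 ml/cm × 2 mg/ml = 2 mg/cm at both sites.

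**Total dose, IPR.** 16 × 2 = 32 mg and 4 × 2 = 8 mg, so 32 + 8 = 40 mg.

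**Total dose, IIR.** Incision length is 1.0 + 1.0 + 0.5 + 0.5 = 3.0 cm, so 3.0 ml and 3.0 × 2 = 6 mg.

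| IIR scenario | Volume (ml) | Dose (mg) | IPR/IIR ratio | Difference (mg) |
|---|---|---|---|---|
| Standard ports | 3.0 | 6.0 | 40/6.0 = 6.7 | 34.0 |
| One 10 mm port widened to 12 mm | 3.2 | 6.4 | 40/6.4 = 6.25 | 33.6 |
| Both 10 mm ports widened to 12 mm | 3.4 | 6.8 | 40/6.8 = 5.9 | 33.2 |
| Whole 5 ml syringe used | 5.0 | 10.0 | 40/10 = 4.0 | 30.0 |

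Two comparisons show the scale. At 2 mg/cm, 40 mg would need 40/2 = 20 cm of incision, against 3 cm at standard ports. The 8 mg placed in the fossa alone exceeds the whole standard IIR dose (8/6 = 1.33).

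**Is the rate itself matched?** Operative Technique Protocol cites a dome length of 32.6 (taken here as cm). Half is 16.3 cm, so 16 ml is 16/16.3 = 0.98 ml/cm, or slightly less if the right side is more than half. That is close to the rule, although one rough length serves every patient while incisions were measured individually. The fossa volume, 4/20 = one fifth of the IPR total, has no stated length, so its rate cannot be checked.

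**The case against.** The strongest defence is that the sentence follows directly from the per-cm rule, whose stated purpose is a uniform comparison at the two locations. Read that way, dosage means amount per cm, and the wording is loose rather than false. The volumes are also disclosed: anyone reading the syringe description can see 20 ml of drug in one group and at most 5 ml in the other. Further, equal milligrams need not be the fairer match. The documents give no dose-response information for either site, and equal totals would need an impractical length of incision. Dosing each site to its own extent is a legitimate comparison of regimens, and a ratio of milligrams does not measure bias in pain scores.

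Much of this stands. Matching by rate is a defensible choice, the regimens need no change, and the effect of the dose difference on pain cannot be sized from these documents. None of it makes the sentence correct. The sentence refers to dosage used in the groups, dosage is nowhere defined as dose per cm, and neither document acknowledges that the totals differ. Even the per-cm reading is undocumented for the fossa. The argument that each site calls for its own volume also supports reading the contrast as one of regimens, which is what the fix asks for.

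**Conclusion.** The statement is wrong as written. Only the nominal rate, 2 mg/cm, is the same. Total ropivacaine is 40 mg in IPR and 6 mg in IIR at standard ports, a ratio of 6.7, and the ratio stays at 4 or above for any IIR dose the prepared syringe allows. The site part of the primary objective is therefore a comparison of site and total dose together.

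This rests on three assumptions: 0.2% means 2 mg/ml; the port sizes were those described; and, for the 10 mg ceiling, no drug beyond the one prepared 5 ml syringe was used. Nothing here shows that the dose difference altered a result. This should be fixed, because it is a factual misstatement bearing on a primary comparison and costs very little to correct.

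**What to change.** Replace the sentence in Operative Technique Protocol with:

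> The nominal rate was the same at both sites (1 ml/cm, 2 mg/cm); total dose was not: 20 ml (40 mg) in IPR and about 3 ml (6 mg, at most 10 mg) in IIR.

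If the measured incision lengths were recorded, add one descriptive line giving the actual IIR volume and dose. Leave the stated objective and the doses as they are. Word the IPR-versus-IIR conclusion as a comparison of the two regimens as given, with the three readings set out above for an IPR advantage, a similar result and an IIR advantage.

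The cost is one methods sentence, the wording of one conclusion and possibly one descriptive line, with no extra patients, procedures or analyses. The price is a more qualified conclusion about site unless IIR proves better.

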### **Post-operative Pain Control Protocol**

Pain control in post-operative patients was in 2 forms:

1. Standard Pain Control: Injection (Inj.) Diclofenac Sodium 75mg/1ml (aqueous) IV 12 hourly was used as standard analgesia in all the patients irrespective of what study group patient belonged to.
2. Rescue Analgesia (RA): Inj. Tramadol 100 mg IV stat was used for providing analgesia at any point of time for those patients who demanded for additional pain relief, in case the pain was very distressing to them. Moreover, all the patients who had a VAS and/or NRS >6 or agonizing pain at any point of time, were offered rescue analgesic, especially at the

0.5th hour when the pain is usually higher. Some patients might still need additional analgesia beyond this point. But the dose of Inj. Tramadol cannot be repeated for the next 6-8 hours due to possibility of drug accumulation/toxicity. So, a dermal patch of Diclofenac Diethyl Amine (Nupatch 100mg/50cm^2; Zydus Cadila, Ahmedabad, India) which is a slow release drug delivery system, was used as a second line of RA. It was offered to all the patients who had already been given Inj. Tramadol and even after 2 hours of its administration as timing of peak effect of Tramadol  $\approx$  2 hours, either the patient had a VAS and/or NRS  $>6$ ; or patient had agonizing pain; or if the patient still asked for additional pain relief.

## **Statistical Analysis**

At the end of the study, the envelopes were opened and statistical calculations were made. Mean and standard deviation were observed for continuous forms of data like age, operative duration, numeric pain scores and so on. Such data was further evaluated for significance by Student t-test (for comparing 2 groups), analysis of variance (ANOVA) (for comparing more than 2 groups) and post-hoc analysis in the form of Tukey's Honest Significance Difference (HSD) test. Tukey's HSD test is more conservative in nature as compared to t-test, so has more value in interpretation of results. So, wherever the findings of t-test and Tukey's HSD test disagreed, the results of latter presided over the former. For categorical data, such as results of VDS, FPS-R, ATS and so on, significance testing is done by Fisher's Exact test (FET). A p-value of less than 0.05 was considered statistically significant for all practical applications. Data analysis was done with *IBM SPSS Statistics*® software version 24.

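### Fisher's exact test ignores the order of the VDS, FPS-R and ATS grades and loses power against a roughly uniform shift in pain

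*SAP*

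**What the plan says.** The primary objective (Protocol, Aims and Objectives) is the effect of ropivacaine "on the intensity of post-operative pain in patients undergoing laparoscopic cholecystectomy", over controls and between two sites of use. Five pain scales serve it, and none is named as primary.

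Three of them are recorded in grades:

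- **VDS** (Protocol, Subjective Scales): "A 7 point subjective scale in which patient was told to indicate it verbally about the perception of pain as experienced", with labels listed from absence of pain to the worst imaginable.
- **FPS-R** (Protocol, Objective Scales): "facial expressions of the patient are assessed by the investigator, as depicted in the Figure 1 and scored accordingly". The figure is not reproduced in the text available, so the number of levels cannot be read.
- **ATS** (same section): labels in rising order, beginning "No Pain / Can Be Ignored / Interferes With Task / Interferes With Concentration". The text announces five grades but six labels follow.

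For these the SAP (Statistical Analysis) says: "For categorical data, such as results of VDS, FPS-R, ATS and so on, significance testing is done by Fisher's Exact test (FET". Pain scores recorded as numbers go to the t-test, ANOVA and Tukey's HSD. No rank test, trend test or ordinal model is named, and no collapsing of grades is described. The SAP does not say whether Fisher's test is run across three arms or in pairs, or separately at each time.

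**The concern.** The question is whether patients have more or less pain. Fisher's test on an arm-by-grade table asks only whether the distributions differ in some way. It spreads its sensitivity over every possible pattern of difference and, beyond two levels, gives no direction.

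If ropivacaine moves patients down the scale by a roughly uniform amount, the effect is more likely to be missed on VDS, FPS-R and ATS than it need be. FPS-R and ATS are also the two scales with investigator assessment. A non-significant result there could be misread as a failure to confirm what patients reported.

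Type I error is not at issue: each single test keeps its 5% level. Multiplicity over scales, times and arm pairs is a separate matter.

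**Working it through.** **1. Why order is lost.** With fixed margins, Fisher's test ranks tables by

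P(table) = (∏ row totals! × ∏ column totals!) / (N! × ∏ cell counts!).

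Reordering the grade columns changes none of these products, so the p-value is the same for any ordering of the grades. A rank test (Mann-Whitney for two arms, Kruskal-Wallis for three) is built from Σ Rⱼ²/nⱼ, where Rⱼ is the sum of midranks in arm j. It changes when the grades are reordered.

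**2. How much of the analysis is touched.** The protocol's Methodology section says "Pain was assessed at 5 points of time in the post-operative period". For ATS, "this scale was not used to assess the patient at 30 minutes post-operative hour", which leaves four times. If each time is tested separately (not stated), VDS 5 + FPS-R 5 + ATS 4 = 14 comparisons. If VAS and NRS are the numeric scores the SAP has in mind (a reasonable reading, but it names neither), they add 5 + 5 = 10. That makes 14 of 24. These are repeated measures of the same pain in the same patients, not 14 independent chances to miss an effect.

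**3. Power under a uniform shift.** The plan states no power figure to reproduce. Assumed: a normal latent pain score cut into evenly used grades, a 0.5 SD shift, two equal arms and two-sided 5%. P-values come from 999 random tables with fixed margins, with 2000 trials per setting (simulation SE at most √(0.25/2000) = 1.1 points). Entries are Fisher / rank power in %.

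| n per arm | 7 grades | 6 grades | 3 grades |
|---|---|---|---|
| 20 | 15.3 / 30.2 | 16.1 / 31.2 | 20.3 / 24.7 |
| 30 | 21.9 / 43.0 | 23.0 / 42.3 | 29.3 / 37.1 |
| 50 | 36.5 / 66.1 | 38.5 / 64.9 | 44.8 / 55.6 |
| 70 | 53.3 / 81.0 | 53.8 / 79.7 | 64.2 / 73.5 |
| 100 | 70.6 / 91.5 | 74.2 / 92.2 | 78.3 / 86.1 |

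The loss (rank minus Fisher) is 15-30 points with 7 grades, 15-26 with 6 and 4-11 with 3. With 2 grades the tests coincide (41.5% each at n = 50).

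**4. Other uniform-shift settings.**

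- *Scores bunched at the low end*, 7 grades, n = 30-100: loss 14-20 points with 50% of controls in the lowest grade, 9-23 with 75%.
- *Three arms* at 0, 0.25 and 0.5 SD, n = 20-100: loss 11-33 points with 6-7 grades, 5-12 with 3, about nil with 2.
- *Proportional-odds model*, odds ratio 2 or 3, 4-7 grades, n = 30-75: loss 7-37 points. The largest is three arms, 7 grades, n = 50, odds ratio 3: 80.5 − 43.5 = 37.

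**5. In patients.** With 7 grades, a rank test at 50 per arm has 66.4% power. Fisher reaches 64.8% at 90 and 67.5% at 95, so it needs about 1.8 to 1.9 times as many. With 3 grades the match is at about 60-65 per arm (rank 57.7% at 50; Fisher 55.5% at 60, 61.5% at 65).

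**6. Is the rank test simply liberal?** No. Under no effect, two-arm rejection was 1.9-5.1% for Fisher and 1.9-4.9% for the rank test. With three arms it was 5.5-5.9% and 5.1-6.1% (simulation SE 0.5 points).

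**7. Where the ranking reverses** (7 grades, two arms unless stated; Fisher / rank power in %).

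| Difference | n per arm | Fisher / rank |
|---|---|---|
| Two worst grades emptied | 30 | 43.8 / 14.4 |
| Two worst grades emptied | 50 | 81.2 / 18.0 |
| Same, three arms, one half-way | 50 | 63.7 / 14.5 |
| Two worst grades halved | 50 | 15.1 / 8.5 |
| SD doubled, no shift | 50 | 62.1 / 6.1 |

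**The case against.** The best counter-argument is that this is a trade-off, not a defect. Nothing in the documents says ropivacaine acts as a uniform shift. Rescue analgesia is offered to "all the patients who had a VAS and/or NRS >6 or agonizing pain at any point of time" (Protocol, Post-operative Pain Control Protocol), which may alter later scores selectively at the top of the scale. The reversals in step 7 are larger than any loss under a uniform shift. Fisher's test is valid, the numeric scores already address intensity by parametric methods, and a change made after the envelopes were opened can only be supplementary. The table layout is also unstated. The protocol bands NRS into four severity classes, so grades might be collapsed, and collapsing shrinks the loss.

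Much of this stands. The shape of the effect is unknown, the sizes above are illustrations, and calling the three scales supporting would be an inference, since the documents rank none. But the objective is about intensity, for which a test that uses order is the natural default. No collapsing is described for these scales. The sensitivity to worst-grade effects can be kept by reporting both analyses.

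**Conclusion.** The concern holds within its limits: more than two grades in use and a roughly uniform change in pain. Fisher's test then discards the ordering on which the objective depends. The principle is certain; the size for this trial is not. Sample size, allocation ratio, effect size and use of grades are all assumed, and the range from nil to 37 points describes the settings run, not a bound. Losses are material if six or seven grades are in real use and small if patients fall into two or three.

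The weight is moderate. Efficiency and direction are lost on three of five scales, no result is invalidated, and the analysis of numeric scores is not affected. The change is worth making because it is cheap, not because the planned analysis is wrong.

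**What to change.** 1. Analyse VDS, FPS-R and ATS by Kruskal-Wallis across the three arms, with exact or Monte Carlo p-values if tables are sparse. Follow with Holm- or Dunn-adjusted pairwise rank tests.
2. Give an effect measure with a 95% CI, such as the probability that a patient in one arm has less pain than a patient in another. This supplies direction and size, which neither omnibus p-value does.
3. Keep Fisher's test for binary or unordered items. For the three scales, report the planned Fisher result and the full arm-by-grade table alongside, so that a reduction confined to the worst grades, or a change in spread, stays visible.
4. State the table layout: all grades or collapsed, three arms or pairs, each time separately or not. Reconcile the number of ATS grades with the labels listed.
5. The SAP reports that calculations were made once the envelopes were opened. A rank analysis added after that point should be labelled post hoc, with Fisher kept as the planned result and no choice between them by p-value.

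The cost is a re-run of three scales and a short text change, with no new data. The statistical price is the rank test's weakness against the differences in step 7, which item 3 limits.

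### No primary pain scale, time or summary is named and nothing controls error across scales and times, so one isolated p < 0.05 could carry the primary conclusion

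*SAP*

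**What the plan says.** **Objective.** The Protocol (Aims and Objectives) sets out to assess "the effect and impact of using the local anesthetic ropivacaine, over controls, on the intensity of post-operative pain", and to compare the intraperitoneal and intraincisional sites. It gives no scale, time or summary measure, and no later section supplies one.

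**Measurements.** Under Methodology, "Pain was assessed at 5 points of time in the post-operative period": 0.5, 4, 8, 12 and 24 hours. The scales sections list five instruments: VAS, NRS, VDS, FPS-R and ATS. Of ATS the Protocol says "this scale was not used to assess the patient at 30 minutes post-operative hour". Rescue analgesia is also recorded.

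**Analysis.** The SAP (Statistical Analysis) assigns numeric pain scores, which I take to be VAS and NRS, to t-tests, ANOVA and Tukey's HSD, with Tukey prevailing over the t-test where they disagree. It assigns VDS, FPS-R and ATS to Fisher's exact test, without saying whether that means one three-group test or pairwise tests. The threshold is "A p-value of less than 0.05 was considered statistically significant for all practical applications". No method combines times, and no adjustment across scales or times is given.

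**The concern.** Because pain intensity is not tied to one measurement, a significant result on any scale at any time can be presented as meeting the primary objective. Each further scale and time is another opportunity for a chance finding at 0.05. At stake are both primary questions: whether ropivacaine relieves pain, and which site is better. Under this rule an isolated p-value just below 0.05 is weak evidence on either.

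**Working it through.** The documents state no familywise error rate, sample size or power, so there is no figure of the plan's own to reproduce.

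**1. Count the cells.**
- Four scales × 5 times + ATS × 4 times = 24.
- VAS and NRS: 2 × 5 = 10 cells.
- VDS, FPS-R and ATS: 5 + 5 + 4 = 14 cells.
- Three arms give 3 pairs per cell, so 24 × 3 = 72 pairwise comparisons.

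**2. Reference values under independence.** With one 5% test per cell, the chance of at least one false positive is 1 − 0.95^m:
- m = 5 (VAS alone): 22.6%
- m = 10 (VAS plus NRS): 40.1%
- m = 24: 70.8%

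Scores from the same patient are correlated, so these values are benchmarks and not estimates.

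**3. Null simulation with correlation.** All inputs here are assumptions:
- no true difference among the three arms; normally distributed scores;
- 20, 40 or 80 per arm;
- correlation between two cells equal to the between-scale r times the between-time r, with pairs (scale, time) of 0.95/0.9, 0.9/0.7, 0.8/0.5 and 0.6/0.3;
- Tukey's HSD at 0.05 within each cell;
- 2,000 simulated trials per setting, so the Monte Carlo standard error is at most √(0.5 × 0.5/2000) = 1.1 percentage points. The rounded ranges also cover repeat runs.

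| Results eligible for the claim | Any false significant pair | False benefit of ropivacaine over control |
|---|---|---|
| VAS, five times | 9%-22% | not reported |
| VAS plus NRS, ten cells | 12%-36% | 4%-15% |
| All 24 cells, if all were numeric with Tukey | 16%-59% | see objection |
| One endpoint: patient's mean VAS | about 5% | 1%-2% |

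The low ends belong to near-duplicate scales and times (0.95/0.9), the high ends to 0.6/0.3. At 40 per arm the 24-cell figures for the four pairs are 16.7%, 29.6%, 40.6% and 56.7%.

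**4. Effect of an ANOVA gate.** If Tukey is read as following a significant ANOVA, the 24-cell rates at 40 per arm fall from 17.5, 28.4, 40.8 and 55.6% to 15.8, 26.3, 37.7 and 52.5% in a separate run of 4,000 trials. That is about 2 to 3 points, and up to about 4 across settings.

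**5. The Fisher cells.** Under a range of assumed category distributions, one three-group Fisher test has a per-cell error of 3.0%-5.2%. Any of three unadjusted pairwise Fisher tests in a cell has 3.8%-12.7%. The 14 categorical cells therefore add to the VAS plus NRS figures, by an amount that depends on a choice the SAP leaves open.

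**The case against.** **The SAP does not order 24 tests.** A reader might infer that every cell is tested, or that one significant cell establishes the objective. Neither is written. The 24-cell family is my construction, and its boundary is debatable, since rescue use is also a pain outcome and is left out. This stands: 16%-59% describes what the rule permits and is not the plan's error rate. The concern survives on the narrowest family, because VAS alone over five times still gives 9%-22%.

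**Tukey's HSD already deals with multiplicity.** It does so for the three arm pairs within one numeric outcome at one time, and the figures above credit it. It does nothing across scales or times.

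**The scales measure nearly the same thing.** That is allowed for: the mildest setting has between-scale r 0.95 and between-time r 0.9.

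**A larger directional harm.** Applying Tukey to all 24 cells at 40 per arm gives a false ropivacaine benefit of 6.2, 12.2, 15.3 and 25.2% for the four correlation pairs. The SAP does not support that reading. It assigns three of the scales to Fisher's test, and a three-group Fisher test has no direction. The supportable figure is the 4%-15% for VAS plus NRS.

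**The study is written up as complete.** Naming an endpoint now cannot restore pre-specification. This also stands, and it limits the fix to honest labelling and re-analysis.

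**Conclusion.** The point holds. No primary pain endpoint is defined, the same 0.05 applies throughout, and error is uncontrolled across scales and times. On the stated assumptions, the chance of some false significant result is about 2 to 4 times 5% if only VAS is used (9/5 = 1.8 to 22/5 = 4.4) and about 2 to 7 times for VAS plus NRS (12/5 = 2.4 to 36/5 = 7.2). The Fisher cells add an unknown amount. These sizes depend on assumed arm sizes and correlations; the direction does not.

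A reader might also infer that the scale and time were chosen once the results were visible. The documents do not show this. The SAP says only that calculations followed the opening of the envelopes; it does not say when, or whether, an endpoint was chosen.

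This should be corrected before any confirmatory claim is made, because it bears on the primary conclusion itself.

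**What to change.** 1. **Name one primary endpoint and give the reason.** One example is each patient's mean of the five VAS scores, compared by ANOVA with Tukey's HSD over the three arm pairs at 0.05. VAS is a continuous measure ("A 10 cm line was used and patient was told to mark on it using a pen"), all five times contribute, and the tests are already in the plan. Report rescue use by arm beside it.
2. **Make the rest secondary.** Report other scales, single times and rescue use with estimates and confidence intervals and no confirmatory claim, so that no second alpha family is opened. State whether Fisher's test is three-group or pairwise.
3. **State whether the endpoint was fixed before the envelopes were opened.** If it was not, label it post hoc. Any confirmatory claim should then come from a single Holm procedure over the 72 unadjusted pairwise p-values (t-tests for VAS and NRS, pairwise Fisher for the others), where the smallest must be at or below 0.05/72 = 0.00069. This replaces the mean-VAS test. Running a mean-VAS test alongside separate Holm families of 24 three-group and 72 pairwise p-values, each at 0.05, gave 4.9, 5.9, 7.0 and 9.2% for any false claim at 40 per arm.

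**Cost.** New wording and a short re-analysis of data already collected. The downsides should be stated:
- Isolated time-point results can no longer be called significant.
- An unweighted mean over unequally spaced times can hide an early effect.
- The Protocol says "all the patients who had a VAS and/or NRS >6 or agonizing pain at any point of time, were offered rescue analgesic", so the four scores after 0.5 hours (4/5 = 80% of the weight) may follow rescue, which can dilute a difference.
- A late choice of endpoint does not restore pre-specification.
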